tDCS Effects on Post-Procedural Pain Pilot:¹⁰² Recently, the PI conducted the first-ever pilot study on the effects of tDCS on post- Endoscopic Retrograde Cholangiopancreatography (ERCP) pain. Nineteen Caucasian females (mean age=37.2 StdErr=2.4) were enrolled. After ERCP, participants were randomly assigned to receive 20-minutes of tDCS with anode over the left-prefrontal cortex and cathode over the gut representation of the sensory cortex. No serious adverse events were associated with tDCS. Side-effects of tDCS were limited to tingling (42%), itching (47%) and mild stinging (11%) under the electrodes. Patients that received a single 20-minute dose of real tDCS used 22% less total hydromorphone than those that received sham at the end of the 24-hour inpatient post-procedural period (Cohen's $d=.38$). The slope of the cumulative PCA usage curve was significantly steeper in the sham tDCS group compared to real ($t(355)=10.80, p<.0001$). VAS pain scores suggested an arithmetic advantage for real tDCS compared to sham (not statistically significant likely due to limited power). *Results from this pilot feasibility study suggest that tDCS is safe, well-tolerated, and may be able to reduce post-ERCP opioid requirements without increasing subjective pain ratings.*

[figure not shown]
tDCS Effects on Post-Total-Knee-Arthroplasty (TKA) Pain Pilot: In a very recent preliminary pilot study, the PI randomly assigned 40 patients undergoing unilateral TKA to receive a total of 80 minutes of real ($n=20$) or sham tDCS ($n=20$) with the anode over the knee representation of the motor strip and cathode over the right dorsolateral prefrontal cortex. 20-minute tDCS treatments were delivered: 1) in the PACU, 2) 4 hours later, 3) the morning of post-operative day-1, and 4) the afternoon of post-operative day-1. VAS pain and mood ratings were collected every 4 hours following surgery provided that patients were awake. The slopes of the cumulative PCA usage curves were significantly different between groups, and those TKA in the real tDCS group used 44% less PCA dilaudid at 48-hours post-op ($p=.007$; Cohen's $d=1.0$). Despite significantly lower PCA dilaudid levels, VAS ratings of pain-on-average were also significantly lower in the real tDCS group ($t(37)=2.28, p=.029$). No adverse events or serious adverse events were encountered. There were no cases in which tDCS needed to be discontinued due to patient discomfort or tDCS-related complications.

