PATIENT CONTROLLED ANALGESIA (PCA) PUMP USAGE: After tDCS administration, patients will be started on a patient controlled analgesia (PCA) pump. For statistical analyses of PCA pump usage, morphine-equivalent analgesic dose will be calculated (e.g., 0.2 mg of hydromorphone = 1.0 mg of morphine). Initial PCA settings will consist of hydromorphone 0.2mg/dose with a lockout interval of 10 minutes. The 4-hour maximum dose will be 4.8mgs with no continuous infusion. If a patient does not tolerate hydromorphone, the PCA medication can be changed to a different opioid and morphine-equivalent dosing will be used. If pain is not adequately controlled, the patient will be reassessed by

study personnel prior to increasing the PCA dosing regimen. PCA pump usage will be downloaded from the PCA pump after discharge from the hospital.

MEDICAL OUTCOMES STUDY SHORT-FORM 36 HEALTH SURVEY (SF-36) is a 36-item measure of general health intended to capture quality of life, functional ability and well-being (mental and physical). The SF-36 will be administered pre-surgery, at discharge, 3-month and 6-month follow-up.

BEST GUESS QUESTIONNAIRE will be used to determine how accurately patients, raters and tDCS operators were able to assess which treatment the patient received. This will assess our success in masking the sham treatments. Any time a guess-confidence rating is greater than 8 (on a 0 to 10 numeric rating scale), the PI will follow-up with the participant and/or administrator in order to determine what factors contributed to this level confidence. If the guess is verified correct by the statistical support personnel and any valid systematic administrative factors are identified (e.g., the participant or tDCS administrator reports that the he/she overheard the device-masking assistant discussing the device configuration, accidentally viewed the randomization codes, or felt/heard some unique tDCS-induced sensations that led them to correctly guess the condition), the participant will remain enrolled in the study (and no feedback will be provided to the administrator or participant regarding whether the guess was correct in order to avoid providing information that may further jeopardize the blind in later subjects). The participant's data will be dropped from analyses and steps will be taken to correct the mask procedure.

Table 1. Overview of the measurement schedule for the proposed study (POD=post-operative day)

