Statistical Analysis and Power: The orthopaedic surgeons at the Ralph H. Johnson VAMC conduct ~100 unilateral total knee arthroplasties and ~50 unilateral total hip arthroplasties each year . Thus, in order to meet the proposed n-size of the current study, 24 (out of 100) participants will need to be eligible and interested in participating in the trial each year. We will over recruit to permit for drop-outs and participants lost to follow-up. For analysis of primary outcomes associated with Aim-1, participants receiving any active tDCS (groups 1,2 & 3) will be collapsed and compared to the sham-only group. Multivariate multiple regression will be used with group-assignment entered into the model as a binary predictor. Surgery and anesthesia duration, depression & anxiety scores, sex, age, pre-tDCS pain, (ROM) Means and pre-op chronic opioid status will be entered into the model as covariates to permit for statistical control of these potentially confounding variables. Overall differences between real and

sham tDCS groups will then be examined for our primary outcomes: total post-op PCA morphine-equivalent dose, VAS pain-on-average ratings, and mean number of post-operative complications. Using the most conservative effect-size estimate from our series of pilot studies ($d=.70$), with 90 patients in the active tDCS group and 30 in the active-sham group, power is good to detect significant effects if they exist ($\alpha=.016$ (corrected for multiple DV's); $1-\beta >.80$; see figure 9). For Aim-2, MANCOVA will be conducted using all 4 groups and all primary dependent measures in the same model (controlling for surgery and anesthesia duration, depression & anxiety scores, pre-tDCS pain, physical rehab measures and chronic opioid status). With four groups of 30 patients each, assuming a moderate effect size $f^2(V)=.2$, and alpha of .05, power is good detect significant main effects in the model ($1-\beta >.80$). Secondary analyses will be conducted to evaluate long-term effects of tDCS on pain, functioning and quality of life (i.e., 2-wk, 4-wk, 8-wk, 3-month and 6 month-follow-up).

Problems/Challenges/Potential Pitfalls: The proposed tDCS device is an FDA-approved iontophoresis device, and its use for tDCS applications is off-label. The tDCS procedure is minimal-risk and FDA-

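### The Aim-1 regression assumes one residual variance in a 90:30 contrast, so if spread falls with the mean, its intervals for PCA dose and complications are too narrow when tDCS works

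*Combined protocol and SAP*

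**What the plan says.** Section D, Statistical Analysis and Power, defines the Aim-1 contrast: "participants receiving any active tDCS (groups 1,2 & 3) will be collapsed and compared to the sham-only group". The method follows: "Multivariate multiple regression will be used with group-assignment entered into the model as a binary predictor", with a list of covariates. The outcomes are "total post-op PCA morphine-equivalent dose, VAS pain-on-average ratings, and mean number of post-operative complications". The power statement is made "with 90 patients in the active tDCS group and 30 in the active-sham group", at d = .70 and alpha .016 per outcome, and claims power above .80.

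Under Dependent Measures, the paragraph on PCA pump usage says: "For statistical analyses of PCA pump usage, morphine-equivalent analgesic dose will be calculated". It stops at that conversion. Nowhere does the document name a transformation, a count model, an unequal-variance or robust standard error, or a check of the variance assumption. It does not mention confidence intervals either.

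**The concern.** Multivariate linear regression with common predictors gives, for each outcome, the same group coefficient and standard error as an ordinary least-squares fit of that outcome alone. Each fit uses one residual variance for both arms. Two of the three outcomes make that assumption doubtful. PCA dose cannot be negative, and a complication count has a variance tied to its mean. If tDCS lowers the mean, the active arm may also be less variable.

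With a 3:1 split this matters. The pooled variance comes mainly from the 90 active patients, while the true uncertainty of the difference comes mainly from the 30 sham patients. The model would then understate the standard error in the situation the trial hopes to find. Sections B and D say the findings will inform whether a larger multi-site trial is needed. An interval that is too narrow would make the opioid-sparing estimate look more precise than it is.

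**Working it through.** **The plan's own figure.** With 90 v 30, d = .70 and two-sided alpha .016 (sidedness is not stated), the noncentrality is .70 × √(90 × 30/120) = 3.32 and the critical value is 2.41. Normal-theory power is Φ(3.32 − 2.41) = .819; the noncentral t gives .808. The claim of more than .80 reproduces under a common SD. Whether d = .70 is the right effect size is a separate question.

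**What the pilots give.** Section C reports 44% less PCA opioid at d = 1.0 (knee pilot), and for the ERCP pilot that the real-tDCS group "used 22% less total hydromorphone than those that received sham at the end of the 24-hour inpatient post-procedural period", at d = .38. Dividing gives a pooled SD of .44/1.0 = 44% and .22/.38 = 58% of the sham mean. No arm-level SD of PCA dose and no complication rate are given, so the SD ratio below is an assumption, shown over a range.

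**Standard-error ratio.** Let r = SD active / SD sham, with the sham SD set to 1.
- Model SE² = [(89r² + 29)/118] × (1/30 + 1/90)
- True SE² = 1/30 + r²/90
- Coverage of a nominal 95% interval ≈ 2Φ(1.980 × model SE / true SE) − 1

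Example, 22% reduction with SD proportional to mean (r = .78, r² = .608): model SE² = .7046 × .04444 = .03132; true SE² = .03333 + .00676 = .04009; ratio = √.781 = .884; coverage = 92.0%.

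| Mean reduction | SD proportional to mean: r, SE ratio, coverage | Variance proportional to mean (Poisson): r, SE ratio, coverage |
|---|---|---|
| 22% | .78, .884, 92.0% | .883, .939, 93.7% |
| 30% | .70, .840, 90.4% | .837, .915, 93.0% |
| 44% | .56, .763, 86.9% | .748, .866, 91.4% |

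**Simulation checks (20,000 runs unless stated).**
- Gamma dose, CV .55, equal-variance interval: coverage 91.7%, 90.2% and 86.2% at 22%, 30% and 44%. A Welch interval gives 94.5–94.7%.
- Lognormal dose with nine covariates (4,000 runs): 92.4%, 91.1% and 86.3%. HC3 gives 94.4–95.4%.
- Gamma dose with reductions of 15%, 30% and 44% across the three active groups: 91.2%.
- Poisson counts with sham means of 0.5 to 2: about 93–94% at 22% and 91% at 44%. Overdispersed counts: about 93% and 88–90%, and Welch restores only 93–94%.

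**When the problem disappears.** With equal SDs at a 44% reduction, coverage is 95.0%. With a 1:1 split at 44% and constant CV, it is 94.7%. With no effect, coverage is about 95% and the planned test rejects at .014–.018 against a nominal .016.

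**Effect on the test.** For a gamma dose at a 30% reduction, with d = .70 on the pooled SD, the planned test rejects in .78 of trials and the Welch test in .63. In that setting a matching 98.4% interval would contradict the planned test in at least .78 − .63 = 15% of trials.

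**The case against.** The strongest objection is that the premise is unproven for the main outcome. A reader might infer that the pilots imply a CV of .54 to .65 and so show the spread falling. They do not: .44/√[(1 + .56²)/2] = .54 and .579/√[(1 + .78²)/2] = .65 follow only after assuming SD proportional to mean. The PCA dose ceiling over four hours could also compress the spread of the higher-use arm. The laboratory pilot in section C shows spread moving with the mean for scalp pain (1.98, SD 2.02, v 0.18, SD 0.27), but that is a different outcome. This stands: for PCA dose the concern is conditional. It does not remove the point for a count.

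A second tempting reading is that log(dose + 1) should be the primary scale because it costs no power. That holds only for lognormal doses (.81 v .79 for raw dose at CV .54 and a 30% reduction). At the same reduction, log v raw power is .69 v .79 for gamma doses, and about .38 v .73 for lognormal doses with 3% zero users per arm. It also changes the estimand: with equal-SD gamma doses, a true 30% fall in the mean shows as about 40% in the ratio of geometric means. The pilots' percentages do not require it, since a mean difference divided by the sham mean is also a percentage.

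Third, the plan specifies tests and no intervals, and it does not itself use the words raw or equal-variance. Both are inferred from the named method and the absence of any alternative. Nothing in the text rules out robust errors, but nothing provides for them.

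**Conclusion.** The point holds as a conditional weakness in estimation. If spread falls with the mean, the Aim-1 standard error is too small whenever tDCS lowers the outcome. For PCA dose with SD proportional to mean, it is about 12%, 16% and 24% too small at reductions of 22%, 30% and 44%, a loss of about 3, 5 and 8 points from nominal 95% coverage. For Poisson counts it is about 6%, 9% and 13% too small, and overdispersion makes this worse. The 44% case comes from a pilot in which every active patient had four sessions; here only one active group in three does, so the milder rows are the more relevant ones.

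A reader might also infer that the primary test is prone to false positives. It is not: under no effect the two arms have the same spread and alpha is kept. The figures apply to the standard error and to any interval built from it.

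**What to change.** - **PCA dose.** Keep the planned linear model, covariates and test. State that the adjusted mean difference, and that difference as a percentage of the sham mean, will be reported with a heteroscedasticity-consistent interval (HC3 or Welch-type; name one). Report the SD by arm. A log-scale analysis may be added as a sensitivity analysis only.
- **Complications.** Use a log-link count model with the same covariates, either negative-binomial or quasi-Poisson (name one in advance), tested at the same .016, and report a rate ratio. Because the linear fits are equivalent outcome by outcome, removing complications leaves the PCA and VAS results unchanged; only a joint test of all three would lose a component.
- **Disagreement rule.** State in advance that the planned test decides significance for PCA dose and that the robust interval describes precision.

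The change is wording in the analysis section, with no new data. The cost is wider intervals, a PCA interval that may sometimes disagree with the test, and a complications result expressed as a ratio.

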The proper control of acute and chronic pain is one of the most important areas in health care. Despite the profound advances in neuroscience over the past 20 years, we still largely use opiate narcotics, much as was done in the Civil War. Total knee arthroplasty (TKA) is one of the most common orthopedic procedures performed ¹. Because the prevalence of arthritis is expected to grow substantially as the population ages ^{2 3}, these procedures are likely to become even more common. Previous reports suggest that TKA improves functional status, and relieves pain in most patients, and the number and the rate of total knee arthroplasties is increasing steadily. While knee pain is often a complaint that precedes TKA, the procedure itself is associated with considerable post-operative pain lasting days to weeks. Adequate postoperative pain control is an important factor in determining recovery time and hospital length of stay ^{4 5 6}. While the technology associated with the TKA procedures themselves has developed rapidly in the past several years, post-operative pain management techniques have not changed substantially in several decades. Primary methods used to manage post-operative pain typically involve systemic opioid or other analgesic drug delivery, and regional blocks. Despite these pain-management strategies, patients still report considerable post-operative pain, and often struggle to complete post-operative physical therapy regimens. Additionally, systemic opioid analgesic use, has associated side-effects that can lead to post-operative complications including but not limited to mental-clouding, confusion, respiratory depression, interactions with other medications, addiction in some cases, fatigue, and gastric motility problems. Further, the TKA procedures along with the associated intraoperative anesthesia protocols have been associated with increased risk for post-operative cognitive problems⁷ especially among the elderly⁸, and current post-operative pain management strategies can exacerbate these problems. For obese TKA patients, apnea is a real concern that systemic opioid use can complicate. These are relevant concerns as the population receiving TKA are more and more likely to be elderly and/or overweight^{8,9}. New analgesic strategies are needed that can be used adjunctively to existing strategies with the potential to reduce reliance on opioid analgesia. Several novel brain stimulation technologies including transcranial magnetic stimulation (TMS) and transcranial direct current stimulation (tDCS) are beginning to demonstrate promise as treatments for a variety of pain conditions ^{10 11 12 13 14, 15}. Electricity has no metabolite or other residue, and can be delivered with minimal discomfort and without problems associated with drug-drug interactions. TMS and tDCS are minimally-invasive and appear effective in the management of chronic pain and experimentally-induced pain^{10, 11, 16-30}. Recently, the PI on this proposal found that high frequency TMS for 20-minutes post gastric bypass surgery was associated with approximately

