VISUAL ANALOGUE SCALE (VAS) RATING SCALES anchored with "no pain" and "worst pain imaginable" will be collected twice daily during the inpatient stay to assess pain at its worst, pain at its least, pain on average, and pain 'right now'. Additionally, participants will rate pain "Unpleasantness" using VAS in order to assess the affective component of the pain experience. The same system will be used to assess changes in mood at its worst, mood at its best, mood on average and mood 'right now' but the anchors will be "extremely depressed, sad or agitated" and "extremely good mood." This VAS method of pain assessment was chosen because it can be administered numerous times each day and it is highly sensitive to changes in pain perception and mood. VAS ratings will be collected immediately prior to, during, and immediately following all physical therapy sessions (inpatient and outpatient) during the 3-month follow-up period.

DAILY PAIN DIARY: The diary will require participants to record their average pain rating, pain at its worst, pain at its least, Activity level, Mood, sleep from previous night, and the number of times prescription pain medications were taken that day. Participants will be asked to fill out this form each day at night for the first 8 weeks post-surgery.

KNEE FLEXION MEASURE: A Gollehon Extendable Goniometer will be used to measure degrees of knee flexion at each post-operative physical rehabilitation visit.

POSTOPERATIVE COMPLICATIONS will be defined as any event, illness or postoperative occurrence that negatively impacts the health, well-being or functioning of the patients enrolled in the trial (including but not limited to headaches, confusion, delirium, nausea, vomiting, infections, and cardio-vascular complications). These events are tracked by medical staff as part of routine care, and the information will be gathered and recorded in the research database as well as length-of-stay at the time of discharge.

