Measure	Admission	PACU	POD-0	POD-1	POD-2	Discharge	2-weeks	4-weeks	8-weeks	3 months	6-months
BDI	X					X				X	X
BAI	X					X				X	X
BPI	X					X				X	X
SF36	X					X				X	X
PCA		X	X	X	X						
VAS		X	X	X	X		X	X	X		
MPQ		X	X	X	X		X	X	X		
Pain Diary							X	X	X		
Complications		X	X	X	X	X	X	X	X	X	X
ROM							X	X	X		
LOS						X					

Anesthesia/Surgical Measures and Procedures: Patients must be scheduled to receive unilateral total knee arthroplasty (total knee replacement) or unilateral total hip arthroplasty (total hip replacement) at the Ralph H. Johnson VAMC, to be done either cemented or cementless, either computer-assisted or conventional. The anatomical approach will be decided-upon by the surgeon based on clinical presentation, but procedure type and device manufacturer information will be recorded to permit statistical control for different procedural and device implications on post-operative pain. Preoperatively, patients will receive sedation of up to 2 mg of midazolam and 100 micrograms of fentanyl for their comfort during regional anesthesia block placement. A peripheral femoral nerve block catheter will be placed utilizing sterile technique (chloroprep, sterile glove and drape) and femoral nerve stimulation (< 0.5mA) with or without under ultrasound guidance. A 20 ml bolus of 0.5% ropivacaine will be given through the block needle prior to nerve block catheter placement. The catheter will then be placed at a depth less than 5 cm passed the needle tip and secured to the skin using sterile occlusive dressings. The patient will also receive a single injection sciatic nerve block with a 20 ml bolus of 0.5% ropivacaine utilizing nerve stimulation (< 0.5 mA) with or without ultrasound guidance. Intraoperative management

will be standardized to a general anesthetic with laryngeal mask airway or endotracheal intubation (isoflurane, fentanyl (up to 250 mcg) and succinylcholine or vecuronium). Reversal of neuromuscular blockade will be performed with neostigmine and glycopyrolate as required. Intra-articular injection of local anesthetics or opioids will not be performed in any patient. The patients will be started on the patient controlled analgesia (PCA) pump for pain. The PCA will be discontinued on post-operative day-2 at which time the patient will be transitioned to po pain medications (oxycodone). Surgery and anesthesia duration will be recorded and post-operative care will be standardized among all subjects as per standard VAMC clinical protocols.

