Procedures and Flow: After determining eligibility and interest, written informed consent will be obtained from participants in the Orthopaedic Surgery Pre-operative clinic. Participants will complete the screening questionnaires and all questions about the study procedures, risks, and benefits will be answered. On the day of surgery, the corresponding Admission questionnaires will be completed. After surgery, participants will be transferred to the post-anesthesia care unit (PACU), awakened, and be hooked-up to standard clinical physiological monitors. Patients will be started on a PCA pump. Pain/mood ratings will be collected and the EEG 10-20 caps will be placed. The anode and cathode placement positions will be marked and the caps will be removed. Sponge electrodes will be soaked in saline, affixed in their rubber electrode casings, attached to the tDCS machine, placed on the scalp, and held in place with Velcro straps. The participant's study ID number and tDCS session number will be entered into the tDCS controller software, linked to the randomization file, and the stimulation session will begin (double-blind). After 20-minutes, the electrodes will be removed and pain/mood ratings will be collected again. Four hours later, the tDCS procedures will be repeated in the participants' hospital room. On post-op day-1, two tDCS sessions will be conducted separated by at least 3 hours. Pain and mood ratings will be collected before and after each tDCS session. Range of motion measurements will be collected before and after each physical therapy session. On the day of discharge, participants will complete the Discharge questionnaire packet. Total length of stay, and post-surgical complications will be recorded. At all follow-up time-points, participants will complete the corresponding measures and opioid use status will be tracked via patient report and verified via chart review.

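### The Aim-1 primary model adjusts for range of motion, which is scheduled only after tDCS has begun, so the treatment effect may be biased in an unknown direction

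*Combined protocol and SAP*

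**What the plan says.** Section D, Statistical Analysis and Power, compares the pooled active groups (90) with sham (30) for Aim 1. After surgery and anesthesia duration and depression and anxiety scores, the covariate list continues: "sex, age, pre-tDCS pain, (ROM) Means and pre-op chronic opioid status will be entered into the model as covariates". The stated purpose is control of potential confounders. No time point, joint or averaging rule is given for the ROM term.

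The places that bear on timing are:

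- **Procedures and Flow**, before the first PACU session: "Pain/mood ratings will be collected and the EEG 10-20 caps will be placed". No ROM is listed among these steps.
- **Procedures and Flow**, later: "Range of motion measurements will be collected before and after each physical therapy session".
- **Dependent Measures, Knee Flexion Measure**: a goniometer "will be used to measure degrees of knee flexion at each post-operative physical rehabilitation visit".
- **Table 1**: the ROM row is marked at 2, 4 and 8 weeks only. Admission, PACU, POD-0 to POD-2 and Discharge are blank.
- **Dependent Measures, VAS**: ratings continue up to "immediately following all physical therapy sessions (inpatient and outpatient) during the 3-month follow-up period", so some therapy is inpatient.
- **Anesthesia/Surgical Measures and Procedures**: "The PCA will be discontinued on post-operative day-2".

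The Aim-2 MANCOVA has a similar undated item in its covariate list: "pre-tDCS pain, physical rehab measures and chronic opioid status".

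**The concern.** A variable measured after randomised treatment has started cannot confound the randomised comparison. It can be a consequence of treatment, a consequence of the outcome, or both, and adjusting for it then removes or adds part of the effect being estimated.

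The plan's own account makes such a link plausible. The introduction and section E.4 both say that "patients still report considerable post-operative pain, and often struggle to complete post-operative physical therapy regimens". If tDCS reduces pain, it may improve therapy and hence ROM.

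At stake is the primary efficacy estimate. If tDCS raises ROM and ROM goes with lower PCA use, a real effect can be missed. If ROM goes with higher PCA use, the effect is inflated. The trial's findings are meant to inform whether a multi-site trial is needed, and a biased estimate in either direction would mislead that decision.

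**Working it through.** **1. Timing.** The first tDCS session is in the PACU straight after surgery. Both descriptions of ROM (therapy sessions; post-operative rehabilitation visits) and Table 1 (2, 4, 8 weeks) place it later. They differ on the exact visits, but none allows a value before the first session. The Table 1 values also follow the end of PCA on post-operative day 2. Inpatient therapy ROM, if taken, could fall inside the PCA window.

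**2. The plan's power figure.** Inputs from Statistical Analysis and Power: 90 vs 30, d = 0.70, alpha 0.016. Two-sided testing is assumed, since the plan does not say.

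- SE of the difference in SD units = √(1/90 + 1/30) = 0.2108
- Noncentrality = 0.70 / 0.2108 = 3.32
- Noncentral t, 118 df: power = 0.808, which agrees with the stated figure of more than 0.80.

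**3. Effect of adjusting for ROM.** Let g be the tDCS effect on ROM in SDs and r the within-arm correlation of ROM with PCA use. Both are assumptions. The true effect on PCA use is −0.70 SD.

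- Adjusted coefficient = −0.70 − r·g
- SE = 0.2108 × √(1 − r²) × √(1 + 0.75 × 0.25 × g²), 117 df
- If ROM is driven only by earlier PCA use, g = −0.70·r and the coefficient is −0.70(1 − r²).

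Example: r = −0.3, g = 0.5 gives −0.70 + 0.15 = −0.55.

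| Case | Effect (size of r 0.3 / 0.5) | Power |
|---|---|---|
| 1. No ROM difference between arms | 0.70 / 0.70 | 0.848 / 0.916 |
| 2. tDCS raises ROM 0.2 SD, r negative | 0.64 / 0.60 | 0.765 / 0.795 |
| 2. tDCS raises ROM 0.5 SD, r negative | 0.55 / 0.45 | 0.591 / 0.488 |
| 3. tDCS raises ROM 0.2 SD, r positive | 0.76 / 0.80 | inflated effect |
| 3. tDCS raises ROM 0.5 SD, r positive | 0.85 / 0.95 | inflated effect |
| 4. ROM driven only by PCA use, either sign of r | 0.64 / 0.53 | 0.760 / 0.655 |

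In case 2, power drops below 0.808 once the ROM effect exceeds about 0.10 SD (r = −0.3) or 0.18 SD (r = −0.5). Below that, the precision gain outweighs the bias for power, though the estimate is still biased.

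In case 4 with a smaller correlation of 0.1 / 0.2, the effect is 0.69 / 0.67 and power is 0.803 / 0.788.

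**4. No true PCA effect.** The nominal rate of falsely declaring benefit is 0.016 / 2 = 0.008.

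- Case 3 raises it to 0.017 / 0.031 at g = 0.2 and to 0.046 / 0.138 at g = 0.5.
- With negative r the same rates apply to falsely declaring harm.
- In case 4 total rejection stays at 0.016: no inflation.

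**5. Check by simulation.** Least-squares fits, 20,000 runs per setting, gave power of 0.589 / 0.482 for case 2 at g = 0.5, and false benefit of 0.045 / 0.135 for case 3 under the null at g = 0.5. For case 4, power was 0.758 / 0.657 with negative r and 0.753 / 0.655 with positive r. All are close to the formulas.

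**The case against.** **A baseline value may have been meant.** The ROM phrase is a fragment, and its neighbours in the list are dated before treatment. That is fair as a reading of intent. But no pre-treatment ROM appears in the text or Table 1, so an analyst following the plan has only post-treatment values to enter. Figure 1 is not available to us; Table 1 makes a hidden baseline unlikely.

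**The assumed correlations may be too large.** The model already adjusts for pre-tDCS pain, mood scores and other factors, so the relevant correlation is partial and may be small. This stands. In the case that best fits Table 1 (case 4), correlations of 0.1 to 0.2 cost almost nothing.

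**The largest figures rest on the least supported inputs.** A 0.5 SD effect on ROM is demanding, because the pooled active arm includes 30 one-session and 30 two-session patients. The false-benefit rates also need a positive ROM-PCA correlation with no PCA effect. A direct tDCS effect during the PCA window needs inpatient ROM, which Table 1 does not show. These figures show what could happen, not what is likely.

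**Later ROM may carry useful baseline information**, such as pre-existing stiffness. True, but it may also carry the effect of treatment, and the model cannot separate the two.

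None of this supplies a reason to keep a post-treatment covariate in the primary model.

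**Conclusion.** The concern holds. As written and scheduled, the Aim-1 primary model conditions on a variable measured only after treatment has begun. Confidence is high on the timing and on the possibility of bias, but not on its direction or size.

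Over the assumed ROM effects of 0 to 0.5 SD and correlations of size 0.3 to 0.5, a true d of 0.70 is estimated anywhere from 0.45 to 0.95. The bias vanishes if tDCS and PCA use both leave ROM unchanged, and adjustment then gains some power. Only the PCA outcome was modelled. The other two listed primary outcomes, VAS pain and complications, were not.

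One further possible harm is not quantified. Only knee flexion has a defined ROM instrument and no rule for missing covariates is stated, so hip patients could drop out of the model. The change must be made for Aim 1. For Aim 2 the same conclusion applies only if its rehabilitation measures are post-operative.

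**What to change.** - Delete the ROM term from the Aim-1 model. State that all Aim-1 covariates are values measured before the first tDCS session, and analyse post-operative ROM only as an outcome.
- If a baseline ROM was intended, say so and schedule a pre-operative measurement defined for both knee and hip patients.
- In Aim 2, define the rehabilitation measures. If they are post-operative ROM or similar, remove them for the same reason.
- Optional, for precision only: add knee versus hip procedure as a covariate, since procedure type is already recorded.

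Deletion is a wording change in the analysis section. It needs no new data and no change in sample size, and unadjusted power remains 0.808 on the plan's assumptions. The baseline alternative adds one pre-operative measurement per patient.
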